Cost-effectiveness of the PRO application versus standard monitoring is assessed with the incremental cost-effectiveness ratio (ICER), i.e. the ratio of net health care costs to net QALYs (Quality Adjusted Life Years). For a description of the data collection and the analysis, see appendix.

Statistical analysis plan of the Health-Related Quality of Life data

Health-related quality of life (HRQoL) measures are secondary endpoints in the ProWide trial and will be reported in a scientific paper published separately from the main paper. The primary endpoints of the HRQoL paper are Physical function (QLQ-C30), Pain (QLQ C-30), HADS-anxiety and overall EQ-5D-5L index score.

The statistical analyses were planned before any evaluation of the data collected in the trial was made.

Data collection

The HRQoL questionnaires are sent to the patients via the Danish public mail system (eBoks) every second months. All patients in the trial have access to the system. Non-respondents receive a reminder after one week. Responses delivered > 30 days after the invitation is sent is categorized as “missing”.

Specific endpoints of interest in the HRQoL analysis

The specific HRQoL scales that will be analyzed in the ProWide study are:

1. Physical function (QLQ-C30)

Rationale: Physical function is considered a PRO surrogate marker for performance status which is an important prerequisite for both toleration effect of medical antineoplastic treatment.

2. Pain (QLQ C-30)

Rationale: Pain is sensitive to change toward progression in cancer and a symptom that can be managed with analgesics. The symptom could then be improved through actions that are a result of the intervention.

3. HADS-anxiety

Rationale: The intervention could improve the sense of security in the patients and potentially reduce anxiety.

4. EQ-5D-5L index score

Rationale: The generic score represents an overall self-assessed health status and will be used report the effect of the intervention on the overall health.

The EQ-5D-5L score will be reported both in the main paper as a mean-score comparison between the two groups at six months and also analyzed in the HRQoL paper as described below.

HRQoL hypothesis

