The HRQoL hypothesis is that the natural course of cancer-related symptom deteriorations can be overall reduced through actions taken on the basis continuous symptom monitoring throughout the study period. It is expected that the overall effect is larger than the effect on time to deterioration. This expectation applies to all the HRQoL endpoint.

Statistical analyses

The HRQoL data will be analyzed using a linear mixed model approach as the primary analysis to compare longitudinal data between study arms. Area Under the Curve (AUC) will be used as a confirmatory analysis. These analyses are based on the assumption that the scores can be considered as continuous variables²⁶.

Statistical significance

The mean EQ-5D-5L score will be reported for both study groups at six months in the main paper as the primary HRQoL endpoint.

The four HRQoL endpoints of primary interest will be analyzed and reported in the HRQoL paper.

A p-value of <.05 will be considered statistically significant.

Minimal Important Differences (MID)

MID will be used to report the proportion of patients with improvement, stable or deteriorating symptoms compared to baseline

Physical function (QLQ-C30) and Pain (QLQ C-30): a 50 % reduction of the expected mean deterioration without the intervention from baseline to time of progression is considered the MID. Based on clinical data from lung cancer patient treated in the department of oncology, Regional Hospital West Jutland, Denmark (to be published) the expected mean deterioration from baseline to progression is 10 points. A 50 percent reduction then corresponds to an MID of five point for this study.

HADS-anxiety: A 1.5-point change in the HADS anxiety score is considered an MID²⁷.

EQ-5D-5L index score: A change of 6 points is considered an MID²⁸.

Compliance and missing data

Reasons for missing data will be categorized as; administrative censoring (patients who have not reached the relevant time point at the time of the analysis), withdrawal and missing for participants still in the study. If the reason for non-compliance is death the data will not be categorized as missing.

Compliance is defined as the ratio between the number of responses and expected responses (death and administrative censoring as the reason for non-compliance are excluded at the specific time points).

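### The HRQoL paper's four primary scales are each judged at p<.05 with no multiplicity rule, so the chance of at least one false positive among them is roughly 9% to 19%, not 5%

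*Combined protocol and SAP*

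**What the plan says.** The section on the statistical analysis plan for the HRQoL data sets the status of these measures: "Health-related quality of life (HRQoL) measures are secondary endpoints in the ProWide trial". It then defines a second level for a separate publication: "The primary endpoints of the HRQoL paper are Physical function (QLQ-C30), Pain (QLQ C-30), HADS-anxiety and overall EQ-5D-5L index score". The list of specific endpoints that follows gives each scale its own rationale but no testing order.

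Under the HRQoL hypothesis heading there is one hypothesis, that symptom monitoring reduces deterioration overall, and it is said to apply to every HRQoL endpoint.

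Under Statistical analyses, the method is "The HRQoL data will be analyzed using a linear mixed model approach as the primary analysis to compare longitudinal data between study arms", followed by "Area Under the Curve (AUC) will be used as a confirmatory analysis".

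Under Statistical significance there are three statements. The main paper has one HRQoL endpoint: "The mean EQ-5D-5L score will be reported for both study groups at six months in the main paper as the primary HRQoL endpoint". The HRQoL paper has four: "The four HRQoL endpoints of primary interest will be analyzed and reported in the HRQoL paper". The decision rule is "A p-value of <.05 will be considered statistically significant".

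Neither the HRQoL plan nor the protocol's Statistics section contains a multiplicity adjustment, a hierarchy, a requirement that all four scales succeed, or a statement that the HRQoL p-values are descriptive.

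**The concern.** Limiting the HRQoL analysis to four scales named in advance is good practice, and its main benefit is that error control becomes cheap. The plan stops short of that step. Four endpoints share the same primary label, serve one hypothesis and are each held to an unadjusted 5% threshold. Nothing says how a mixed result is to be read. If one scale of four reaches p<.05, the plan as written lets it be reported as a significant primary HRQoL result, with no sign that four chances were taken.

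What is at stake is the strength of the HRQoL claim in its own paper. The trial's main conclusion on survival does not depend on it.

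**Working it through.** **Inputs from the documents.** Four primary scales (HRQoL analysis plan, opening section, repeated under Statistical significance). A threshold of 0.05 for each, unadjusted (Statistical significance). A linear mixed model as the primary analysis, with AUC as a second analysis (Statistical analyses).

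**Assumptions.** Tests are two-sided; the plan says so for overall survival but is silent for HRQoL. There is one between-arm test per scale. No scale has a true effect. The four test statistics have a common correlation rho. The documents give no value for rho, so a range is shown.

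The plan states no family-wise error rate, so there is no figure of its own to reproduce. The sample-size calculation concerns overall survival and does not enter here.

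**Step 1, independent scales.** Chance of at least one p<.05 = 1 − 0.95^4 = 1 − 0.8145 = 0.185.

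**Step 2, correlated scales.** With c = 1.96, the chance is 1 − ∫ φ(u) [Φ((c − √rho·u)/√(1 − rho)) − Φ((−c − √rho·u)/√(1 − rho))]^4 du, by numerical integration. The same integral at the two-sided 0.0125 critical value gives the rate under Holm, since under the global null Holm rejects something only if the smallest p-value passes 0.05/4. The third column counts only false positives favouring the intervention, where a single test has 2.5%.

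| rho | At least one p<.05 | Multiple of 5% | Favouring intervention only | At least one rejection under Holm |
|---|---|---|---|---|
| 0 | 18.5% | 3.7 | 9.6% | 4.9% |
| 0.3 | 17.4% | 3.5 | 8.7% | 4.7% |
| 0.5 | 15.6% | 3.1 | 7.8% | 4.3% |
| 0.7 | 13.0% | 2.6 | 6.5% | 3.7% |
| 0.9 | 9.4% | 1.9 | 4.7% | 2.6% |

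**Step 3, where rho is likely to lie.** The EQ-5D-5L form in the appendix asks about mobility, self-care, usual activities, pain or discomfort, and anxiety or depression. It therefore overlaps all three other scales. Positive correlation is to be expected, and the independent case is an upper limit rather than a central estimate. Even at 0.9 the rate is nearly double the nominal level.

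**Step 4, cost of Holm.** A scale with 80% power at two-sided 0.05 has an expected test statistic of 1.960 + 0.842 = 2.802. The critical value at two-sided 0.0125 is 2.498. Power at Holm's first step is Φ(2.802 − 2.498) = Φ(0.304) = 0.62.

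**The case against.** The strongest reply is that these are secondary endpoints. The trial has one primary endpoint, overall survival, and whether secondary endpoints need family-wise control is a matter of choice. Each scale has its own rationale, so the four can be read as separate questions. Selective reporting is already limited: the scales, the primary model and the minimal important differences are all fixed in advance, and the plan states that the analyses were set before any evaluation of the data.

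Much of this stands, and it bounds the point. It does not remove it. The plan calls the four scales primary for a dedicated paper, ties them to one hypothesis and attaches a significance rule, which invites a confirmatory reading. Labelling the p-values descriptive would answer the concern, but the plan does not do so. AUC does not help either: it reanalyses the same scores, and significance is not made conditional on it.

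Some stronger readings are tempting, and the documents do not support them:

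- **That the trial's own type I error is inflated.** HRQoL is declared secondary, and the overall survival test is separate.
- **That the plan adopts an any-one-of-four success rule.** It states no success rule at all. The gap permits such a claim but does not prescribe it.
- **That the six-month EQ-5D-5L mean is a fifth test, giving 1 − 0.95^5 = 22.6%.** That figure needs independence. The six-month mean uses the same instrument and patients as the longitudinal EQ-5D-5L analysis, with overlapping data, and it is assigned to the main paper.
- **That the lack of blinding makes this worse.** The documents do not use the term open-label, although the intervention is visible to patients. Reporting bias is a separate matter that a multiplicity adjustment does not address.
- **That the main paper's EQ-5D-5L endpoint already acts as a gatekeeper, or could simply be made one.** The plan does not link it to the four scales. What it names is a six-month mean, not the mixed-model effect, so using the latter as a gate would substitute a different analysis.

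**Conclusion.** The concern holds within the HRQoL paper. Four unranked primary scales, each at an unadjusted 5%, give a family-wise error of 18.5% if independent, 15.6% at a correlation of 0.5, 13.0% at 0.7 and 9.4% at 0.9, about 2 to 4 times nominal. These figures assume two-sided tests, one test per scale, no true effect on any scale and a common correlation that the documents do not give. A narrower statement of 13% to 19% would hold only for correlations up to about 0.7.

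The consequence is confined to how a significant HRQoL scale should be read. It is worth correcting because the remedy is short and the plan itself applies the primary label.

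**What to change.** Under Statistical significance, replace the p<.05 rule for the HRQoL paper with a sentence to this effect: the four linear mixed-model treatment effects (physical function, pain, HADS-anxiety, EQ-5D-5L index), one between-arm contrast per scale, are tested by Holm's procedure at a two-sided family-wise level of 5%, and AUC results are supportive only.

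Holm compares the ordered p-values, smallest first, with 0.0125, 0.0167, 0.025 and 0.05, stopping at the first failure. Keep the six-month EQ-5D-5L mean as the single HRQoL endpoint of the main paper, and state that it lies outside this family.

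The cost is one sentence and some power. An isolated effect on one scale with 80% power at 0.05 has about 62% at the first step. The loss is smaller when several scales respond, because later thresholds relax. The documents contain no power calculation for HRQoL, so the actual power on each scale cannot be stated from them.

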To examine the participants quality of life during the study period and at the time of relapse/progressive disease, patients in both arms will be asked to fill in the health-related quality of life (HRQoL) questionnaire every 2 months. The HRQoL questionnaires used are the EORTC QoL-30/LC13 and HADS questionnaire. EORTC-QoL-30 is a questionnaire containing 30 questions with five functional scales (physical function, role function, cognitive function, emotional function and social

function), three symptom scales (tiredness, nausea/vomiting, pain), a global health question and questions regarding frequent symptoms among cancer patients, such as dyspnea, sleep disturbances, loss of appetite, obstipation and diarrhea. The EORTC-QoL-30 also contains a question about financial difficulties. All scales will be linearly transferred to a score between 0-100. For functional scales and global health question, a score of 100 represents the best possible function, while a score of 100 on a symptom scale represents the worst possible symptom. A change in the score by 10 or more is considered a clinically significant change²⁰. LC13 is a supplementary questionnaire to the QLQ-C30 and includes 13 lung cancer-specific questions.

The HADS (The hospital anxiety and depression scale) is a fourteen-item scale. Seven items relate to depression and seven to anxiety. The tool has been developed for detection of anxiety and depression in patients with physical health problems. All items are scored from 0-3 with a possible total score between 0 and 21 for anxiety and depression respectively⁸.

Bjelland et al²¹ identified, in a systematic review, a cut-off point of 8/21 for anxiety or depression. For anxiety, the specificity was 0.78 and the sensitivity 0.9. For depression a specificity of 0.79 and a sensitivity of 0.83 was determined.

The generic EQ-5D-5L⁷ questionnaire will be used to assess quality-adjusted life years (QALY) for a health economic evaluation (*see statistics for details*).

Study design

The study is a multicenter randomised phase III study. After signing informed consent, the patient will be randomized in 1:1 fashion, to the *standard of care arm*, with planned CT-scans according to a standard schedule and measurement of quality of life every 2 months, or to the *experimental arm*, adding weekly PRO monitoring and quality of life measurements to standard of care.

Study population

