APPENDIX

Table 1. Study plan for the randomized clinical trial testing weekly PRO responses

	At baseline	At every CT eval.	At progression*
Histology	(x)		
Disease stage	x		
Charlson's comorbidity index	(x)		
Prior treatment	x		
Maintenance treatment	x		
Clinical examination	x	x	x
Performance status	x		x
Quality of life (every 2 months)	x		
CT-scan	x	-	-
Treatment type after progression			x
Weekly PRO (only the intervention group)	x	-	-

* Patients exit the study when progressive disease has been determined
 (x) data is extracted from central registry

EORTC QLQ-C30 (version 3.0)

Vi er interesserede i at vide noget om Dem og Deres helbred. Vær venlig at besvare alle spørgsmålene selv ved at sætte en ring omkring det svar (tal), som passer bedst på Dem. Der er ingen "rigtige" eller "forkerte" svar. De oplysninger, som De giver os, vil forblive strengt fortrolige.

	Slet ikke	Lidt	En del	Meget
1. Har De nogen vanskeligheder ved at udføre anstrengende aktiviteter, som f.eks. at bære en tung indkøbstaske eller en kuffert?	1	2	3	4
2. Har De nogen vanskeligheder ved at gå en lang tur?	1	2	3	4
3. Har De nogen vanskeligheder ved at gå en kort tur udendørs?	1	2	3	4
4. Er De nødt til at ligge i sengen eller at sidde i en stol om dagen?	1	2	3	4
5. Har De brug for hjælp til at spise, tage tøj på, vaske Dem eller gå på toiletet?	1	2	3	4

I den forløbne uge:

	Slet ikke	Lidt	En del	Meget
6. Var De begrænset i udførelsen af enten Deres arbejde eller andre daglige aktiviteter?	1	2	3	4
7. Var De begrænset i at dyrke Deres hobbyer eller andre fritidsaktiviteter?	1	2	3	4
8. Havde De åndenød?	1	2	3	4
9. Har De haft smerter?	1	2	3	4
10. Havde De brug for at hvile Dem?	1	2	3	4
11. Har De haft besvær med at sove?	1	2	3	4
12. Har De følt Dem svag?	1	2	3	4
13. Har De savnet appetit?	1	2	3	4
14. Har De haft kvalme?	1	2	3	4
15. Har De kastet op?	1	2	3	4

I den forløbne uge:

	Slet ikke	Lidt	En del	Meget
16. Har De haft forstoppelse?	1	2	3	4
17. Har De haft diarré (tynd mave)?	1	2	3	4
18. Var De træt?	1	2	3	4
19. Vanskeliggjorde smerter Deres daglige gøremål?	1	2	3	4
20. Har De haft svært ved at koncentrere Dem om ting som f.eks. at læse avis eller se fjernsyn?	1	2	3	4
21. Følte De Dem anspændt?	1	2	3	4
22. Var De bekymret?	1	2	3	4
23. Følte De Dem irriteret?	1	2	3	4
24. Følte De Dem deprimeret?	1	2	3	4
25. Har De haft svært ved at huske?	1	2	3	4
26. Har Deres fysiske tilstand eller medicinske behandling vanskeliggjort Deres familieliv ?	1	2	3	4

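### The 5-point MID for physical function and pain is a halved group mean used to class individual patients; it lies below one step of either scale and is not reconciled with the protocol's 10-point criterion (minor)

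*Combined protocol and SAP*

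**What the plan says.** Under Minimal Important Differences (MID), in the analysis plan for the HRQoL data, the rule for physical function and pain is that "a 50 % reduction of the expected mean deterioration without the intervention from baseline to time of progression is considered the MID". Departmental data supply the input: "the expected mean deterioration from baseline to progression is 10 points". The result is "A 50 percent reduction then corresponds to an MID of five point for this study".

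The same section gives the purpose: "MID will be used to report the proportion of patients with improvement, stable or deteriorating symptoms compared to baseline". That is a classification of single patients.

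The description of the questionnaires under Implementation of the intervention says of QLQ-C30 scores: "A change in the score by 10 or more is considered a clinically significant change". It also gives the scaling: "All scales will be linearly transferred to a score between 0-100". Neither section refers to the other.

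**The concern.** Three things do not fit together.

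- **Derivation and use.** Half of an expected mean decline describes how much average deterioration the intervention might prevent. It is a group-level target and does not show what change matters in one patient.
- **Resolution.** A cut-off below the smallest possible change cannot separate small changes from important ones. Every net shift of one response category becomes an improvement or a deterioration.
- **Two thresholds.** The same questionnaire carries a 5-point and a 10-point criterion, with no statement of which applies to individuals.

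At stake is how the proportions improved, stable and deteriorated will be read for physical function, one of the four main scales of the HRQoL paper.

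**Working it through.** **Inputs.** The MID, the expected decline and the 10-point criterion are as quoted. Items have four levels scored 1 to 4, so each has a range of 3 (QLQ-C30 form in the Appendix, response columns "Slet ikke Lidt En del Meget"). No scoring key is printed. From the item wording, physical function is taken as items 1 to 5 (item 1 opens "Har De nogen vanskeligheder ved at udføre anstrengende aktiviteter") and pain as items 9 and 19.

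**The plan's figure.** 0.5 × 10 = 5 points, as stated.

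**Scale steps.** A scale of k such items, rescaled linearly to 0–100, moves in steps of 100/(3k).

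| Scale | Items | Step | Changes below 5 | Changes below 10 | Smallest change counted at 10 |
|---|---|---|---|---|---|
| Physical function | 5 | 100/15 = 6.67 | 0 only | 0 and 6.67 | 13.33 |
| Pain | 2 | 100/6 = 16.67 | 0 only | 0 only | 16.67 |

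The two thresholds therefore disagree only for a one-step change (6.67) on physical function. The result does not hang on the exact item mapping: six items give a step of 5.56 and seven give 4.76, so a step of 5 or less needs at least seven items.

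**Exception.** The half rule under Imputation allows a scale to be scored from some of its items. If different numbers of physical function items are answered at the two visits, small non-zero changes can occur: 1.67 or 3.33 (4 v 5 items), 2.22 or 4.44 (3 v 5), 2.78 (3 v 4). Pain has no such exception.

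**Chance changes on physical function.** Assume no true change, five independent items, no floor or ceiling, and each item moving one category up or down with total probability p. The values of p are assumptions.

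| p | Classed as changed, 5-point rule | Classed as changed, 10-point rule |
|---|---|---|
| 5% | 21.5% | 1.1% |
| 10% | 37.3% | 3.9% |
| 20% | 56.8% | 11.9% |

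For p = 5%, the probability of zero net change is 0.95⁵ + 10 × 0.05² × 0.95³ × 0.5 + 5 × 0.05⁴ × 0.95 × 0.375 = 0.785, which leaves 21.5%.

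**Effect on the arms.** Take the plan's own scenario for physical function: a mean decline of 10 points in controls and 5 with the intervention. Assume normally distributed changes rounded to 6.67-point steps, with SD 10 to 25 (the documents give none). Deterioration by at least one step means an unrounded change below −3.33; by at least two steps, below −10. With Φ the normal distribution function, the proportions deteriorated are:

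- one step: Φ(6.67/SD) in controls, Φ(1.67/SD) with the intervention;
- two steps: Φ(0) = 50% in controls, Φ(−5/SD) with the intervention.

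| SD | Control, one step | Control, two steps | Arm difference, one step | Arm difference, two steps |
|---|---|---|---|---|
| 10 | 74.8% | 50% | 18.1 points | 19.1 points |
| 15 | 67.2% | 50% | 12.7 points | 13.1 points |
| 20 | 63.1% | 50% | 9.7 points | 9.9 points |
| 25 | 60.5% | 50% | 7.9 points | 7.9 points |

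Arm differences were taken before rounding. The absolute proportions shift by about 11 to 25 percentage points, and the contrast between arms by at most 1.

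**The case against.** **The reach is narrow.** Statistical analyses makes the linear mixed model primary and AUC confirmatory, both on continuous scores, and no test or decision is tied to the MID proportions. This stands, and it limits the severity.

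**The sections need not conflict.** The 10-point sentence is a general description of the questionnaire and prescribes no analysis. The 5-point value is specific to this study and has a stated derivation, so the analysis plan can be read as governing. A reader might infer that the documents prescribe two rival results for the same data, but they do not go that far. What remains is an unreconciled pair of thresholds.

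**Noise affects both arms.** A reader might infer that counting one-step changes blurs the treatment comparison. The scenario above does not support this: the arm difference is nearly the same under either rule. The chance figures also rest on item-shift probabilities that no document supplies.

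**Pain gains nothing.** A reader might expect the 10-point rule to repair both scales. For pain it does not change a single classification.

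**A stricter rule has a price.** Two steps (13.33 points) exceed the whole expected mean decline, and a loss of 6.67, two-thirds of that decline, would count as stable. This also stands, and it is the reason to show the one-step classification alongside.

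**Conclusion.** The point holds in limited form and is minor. A value derived from a group mean is applied to individuals, and it lies below the resolution of both scales. With complete items, stable means an identical scale score. The 10-point criterion for the same questionnaire is left unreconciled.

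The practical consequence is confined to the absolute proportions for physical function. Measured against the protocol's own 10-point criterion, both improvement and deterioration are inflated, because every net one-step change is counted. The step sizes rest only on the printed form and the item mapping. The sizes of the inflation rest on the assumed SDs, normal changes and item-shift probabilities. The continuous HRQoL analyses, overall survival and sample size are not affected.

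**What to change.** In the MID section of the HRQoL analysis plan:

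- keep 5 points only as the reference for the between-arm mean difference in the mixed model;
- class individual patients by the 10-point criterion already in the protocol, stated in whole steps: at least two steps (13.3 points) for physical function and at least one step (16.7 points) for pain;
- report the one-step (6.67-point) classification of physical function as a sensitivity table;
- cross-refer to the questionnaire description, so that it is clear which threshold serves which purpose.

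The cost is a change of wording and one extra table, with no new data. The downside is that a one-step change on physical function counts as stable in the main table, which the sensitivity table makes visible.

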A first look on the data before doing the HRQoL analysis will define the cut of point of the analysis according to the following rule. Data obtained from baseline up to 12 months will be analyzed as long as the compliance is at least 50 % in both study arms.

A supplementary analysis will explore potential differences in the HRQoL endpoint between patient with high or low compliance and the dropout rates will be compared between study arms.

Imputation

EORTC QLQ C30/L13

If at least half the items used in a scale are available, the mean scores of these items are imputed to the remaining missing items to calculate the specific scale. If more than half of the items in a scale are missing, this whole scale will be considered missing for the individual patient. This approach (the half rule) is recommended in the EORTC QLQ scoring manual^{5,6}.

Multiple imputation will not be used to adjust for missing data.

Ethics

All patients must give their written consent prior to the study according to local ethical standards and all data will be treated with confidentiality. The study has been approved by the Danish Data Protection Agency. Permissions to withdraw data from DLCR will be obtained.

Both study arms will be offered the CT-scans and clinical evaluations according to standard procedures. In the study presented by Denis et al.², patients in the experimental arm were offered less regular prescheduled CT-scans than control arm, which is not the case in the present study.

Perspectives

The French randomized trial of incorporating PRO data in the follow up of lung cancer patients has shown compelling evidence of a substantial improvement in median and overall survival by using a web-application mediated follow-up⁵. If this Danish adaption of the study shows similar positive results it holds great promise for the future strategy for lung cancer follow-up/response evaluation – and possibly also perspectives for improving follow-up for other cancer patients.

In Denmark there is a unique chance to conduct clinical trials of follow up due to the free and equal access to health care, and the possibility of complete follow up by use of the civil registration number, allowing for linkage between registries, a very low rate of patients lost to follow up and often high completeness of data, leading to good data quality.

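### The planned high/low compliance comparison of HRQoL mixes time on study with non-response, because forms due after death leave the compliance denominator

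*Combined protocol and SAP*

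**What the plan says.** All of this is in the combined protocol and SAP, mostly in the HRQoL statistical analysis plan.

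- **Definition** (Compliance and missing data): "Compliance is defined as the ratio between the number of responses and expected responses". A parenthesis adds that "death and administrative censoring as the reason for non-compliance are excluded at the specific time points".
- **Deaths:** "If the reason for non-compliance is death the data will not be categorized as missing".
- **Recorded reasons for missing forms:** administrative censoring, then "withdrawal and missing for participants still in the study". Progression is not a category.
- **Arm-level use of compliance:** data from baseline to 12 months are analysed "as long as the compliance is at least 50 % in both study arms".
- **The split:** "A supplementary analysis will explore potential differences in the HRQoL endpoint between patient with high or low compliance". The same sentence adds that "the dropout rates will be compared between study arms".
- **Imputation:** "Multiple imputation will not be used to adjust for missing data".

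The primary HRQoL analysis is a linear mixed model, with area under the curve as confirmation. Forms are sent every two months, so seven fall between baseline and month 12. The Study period section and the footnote to Table 1 say that patients leave the study at progression.

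**The concern.** Leaving deaths out of the denominator is sensible when reporting completion at a visit, because a dead patient cannot return a form. The difficulty comes from using the same ratio to sort patients. A patient who dies in the second month has one form due; a 12-month survivor has seven. Returning everything is much easier in the first case, so the high group collects early deaths, whose scores are likely to be poor, alongside the patients who did best.

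The mixed model relies on missing forms not depending on unseen scores, given what was observed. A reader would look to this comparison for a picture of how completeness relates to health, since no other planned analysis sets scores against completeness. If the grouping also reflects survival, that picture is distorted. Survival is the primary endpoint and is assumed to differ by arm, so the make-up of the groups would differ by arm too.

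**Working it through.** **Inputs.** One-year survival of 50% (control) and 63.2% (experimental) from the Power calculation section; forms at months 0, 2, …, 12; compliance as defined above, applied per patient. The plan gives no response rate for these forms, no cut-off and no survival shape, so those are assumptions.

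**The plan's own figure.** There is none for this split. The sample size that uses the same survival rates reproduces: a two-proportion calculation gives 221 per arm, 221/0.90 = 245.6, rounded up to 246, and 2 × 246 = 492.

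**How common early death is.** With exponential survival, the share dead before month t is 1 − S^(t/12), where S is one-year survival.

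| Dead before | Control | Experimental |
|---|---|---|
| Month 2 | 1 − 0.50^(1/6) = 10.9% | 1 − 0.632^(1/6) = 7.4% |
| Month 4 | 1 − 0.50^(1/3) = 20.6% | 1 − 0.632^(1/3) = 14.2% |
| Month 12 | 50.0% | 36.8% |

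A Weibull curve with assumed shape 1.5 through the same one-year rates gives 4.6% and 3.1% before month 2.

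**Who is 100% compliant when non-response is purely random.** Assume 80% response per form, control-arm exponential survival, and baseline always returned.

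- Death before month 2: one form due, already returned, so 100%.
- Death in months 2 to 4: one further form due, so 80%.
- All deaths before month 4: 10.9/20.6 = 0.53 fall before month 2, so 0.53 × 1 + 0.47 × 0.80 ≈ 0.91.
- 12-month survivors: 0.8^6 = 0.26.

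If baseline can also be missed, the figures are 0.53 × 0.80 + 0.47 × 0.64 ≈ 0.72 and 0.8^7 = 0.21. This step needs no assumption about health.

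**Effect on the split under purely random non-response.** Here a link between score and death is needed. Differences are high minus low on a 0–100 scale (higher is better). The correct answer for non-response alone is 0.

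| Assumptions | High minus low |
|---|---|
| 75% response, cut-offs 75% to 100%, frailty linking score and hazard (baseline scores) | −1.3 to −4.9 |
| 80% response, cut-off 80%, score falling by up to 15 points in the 6 months before death; baseline always returned | −2.3 |
| As above, baseline can be missed | −1.4 |
| 90% response, cut-off 80%, SD 20, two frailty strengths | −0.4 to −0.7 |
| As above, cut-off 100% | −2.9 to −5.7 |

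**Effect when non-response depends on score.** This uses the second row's assumptions. The slope is the change in log-odds of response per 10 points.

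| Slope | Planned split | 12-month survivors only | Bias in observed mean |
|---|---|---|---|
| 0 | −2.3 | about 0 | 0 |
| 0.05 | −0.8 | +1.8 | 0.3 |
| 0.10 | +1.0 | +4.0 | 0.5 |
| 0.50 | +9.9 | +14.5 | 2.7 |

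If baseline can be missed, slopes of 0.05 and 0.10 give +0.3 and +2.1 in the split, against +2.1 and +4.0 in survivors.

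Survivors all have seven expected forms, so equal denominators remove the artefact. At slope 0.50 the split keeps 9.9/14.5 = 68% of the survivors' difference.

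**The case against.** Several objections carry weight.

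- **Per-patient use is an inference.** The plan describes the ratio at specific time points and applies it at arm level for the 50% rule. It never says that this ratio defines high and low. That stands, but no other definition is offered, and the gap itself needs closing.
- **Progression is left out of the arithmetic above.** If forms after progression remain expected and go unreturned, patients who progress move towards low compliance, against the direction shown. If they are not expected, exit at progression shortens the denominator as death does. The direction is therefore open, but either way the split reflects time on study.
- **The sizes are soft.** Most of the artefacts are below the plan's five-point MID for physical function and pain. With 90% response (the feasibility study's figure for the weekly questionnaire) and an 80% cut-off they are under one point. In the masked cases the bias in observed means is only 0.3 to 0.7 points. This stands and limits the importance of the point.
- **The stakes are low.** The analysis is exploratory, concerns secondary endpoints in a separate paper, and drives no stated decision.

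A reader might also infer that this is the only check on missing HRQoL data, or that every early death counts as fully compliant. The documents support neither. Dropout rates are compared by arm and reasons are categorised. A patient who skipped the only form due scores 0%.

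**Conclusion.** The point holds as a weakness in a supplementary analysis. On the natural reading of the definition, the high/low grouping depends on time on study as well as on willingness to respond. It can show a difference when forms are missing purely at random, and it can dilute or mask a mild dependence on score. Under random non-response the artefact ranged from about 0.4 to 5.7 points across the simulations. That range is illustrative: it rests on assumed response rates, cut-offs, survival shape and strength of the link between score and death, and exit at progression was not modelled. The definitional mechanism does not need those values.

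Two stronger conclusions are not supported. The split does not hide strong informative non-response, which it only dilutes. Nor does its weakness show that the mixed model is invalid: no comparison of observed scores, including the replacement below, can test dependence on unseen scores. Ruling out multiple imputation does not change this, because a mixed model already uses the available forms under missing-at-random.

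**What to change.** Replace the high/low split with a table or figure of mean observed scores up to the last form, by time of and reason for that form and by arm. Use the reasons already recorded (administrative censoring, withdrawal, missing while still in the study) and add death and exit at progression. State whether forms after progression are expected.

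If a compliance split is kept, fix the cut-off in advance and compare only patients with the same number of expected forms, for example those alive and in the study at a landmark. Keep the present ratio for reporting completion rates.

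In either case, present the result as a description of missingness patterns, not as a test of whether missingness depends on unseen scores.

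The cost is a short SAP edit and one table or figure, from data the trial already plans to collect. The drawback is more and smaller groups than a two-way split.
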